8. Referrals and multi-disciplinary team working/ single point of contact, continuity of general practitioner (GP) care, rotating staff across environments to bring new learning, out of hours care from GP's who know patients.

The likelihood of successful implementation of our new enhanced care model requires that we understand the sociological theory underlying how our intervention would operate in practice (19). Following the RAM process, we scrutinised retained intervention components and mapped them to the theories described by Grol (19), categorising them according to which of the four operational levels identified by Ferlie and Shortell (20) and others such as Greenhalgh (21). We thought the components might operate on; 1) individual, 2) team, 3) group and 4) system levels. We explored both impact and process theories, operational and utilisation plans at the levels of the individual, social interaction, organisational context and economic/political context.

Details of the enhanced model of care for piloting are presented below (page 16 and Appendix 1).

AIMS AND OBJECTIVES OF PILOT STUDY

Our aim is to conduct a naturalistic pilot study to understand how the Compassion enhanced model of care operates in practice in two care homes in two different health and social care economies; one in the Camden Commissioning Group and one in the Barnet Commissioning Group.

Objectives

In the pilot study we will provide a coordinator with clinical skills- an “Interdisciplinary Care Leader (ICL)” who will coordinate and support the existing team of health and social care professionals working with participating care homes to enhance the management of people with severe memory problems. Our objectives will be met by collecting both quantitative data and qualitative data from the enhanced care team, care home staff and family caregivers

Specific objectives of the pilot study will be to:

1. Understand whether the enhanced model of care is feasible in the setting
2. Determine whether the enhanced model of care is acceptable to staff and family carers of people with severe memory problems in the care home
3. Understand facilitators and barriers to the implementation of the enhanced model of care by collecting qualitative data from paid and family carers on the experience of the intervention

4. Evaluate whether the enhanced model of care has an impact on a range of national key performance indicators and outcomes including those operating at a number of levels:

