3. If the personal consultee is visiting the care home they will be approached by the care home manager and given verbal information and a written information sheet about the study. They will be encouraged to consider the person’s prior wishes or thoughts regarding taking part in research. They will be asked to sign and return a reply slip indicating if they give consent for their contact details to be passed to the research team. If no reply slip is returned to the research team within 14 days, the research team will contact the care home to inform them of this. The care home will then contact the family carer only once and ask if they agree to the home giving the research team their contact details so the research team can contact them regarding the study. If the family carer does not give permission for the care home to give their details to the research team, no further contact will be made. If permission is granted a member of the research team will telephone the family carer. If the personal consultee agrees to the person taking part they will be sent an information sheet and a family carer assent form to sign or be invited to visit the care home and meet with the research team to do this in person. If no assent form is returned within 14 days then the research team will telephone the personal consultee on the maximum of two occasions to see whether they are still interested in participating.
4. If the personal consultee is not available in the care home (i.e. lives a distance from the home or is not able (or wishes) to visit) the care home manager will post the study information sheet to them. They will also be sent a reply slip to sign and return on whether they give permission for the care home to pass their contact details onto the research team. If no reply slip is returned to the research team within 14 days the research team will contact the care home to inform them of this. The care home will contact the family carer only once and ask if they agree to the home giving the research

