The manual describes in detail processes which aim to improve end of life care for people with severe memory problems by:

- Enabling holistic individualised person centred care.

- Providing an interdisciplinary care leader (ICL) who will act as a central resource for health care professionals, care home staff and family carers involved in the care of people with severe memory problems.
- Developing links and joint working between all those involved in the care and management of people with severe memory problems to establish a model of integrated care.
- Improving the understanding of what is meant by an individualised personal care plan and how such a plan might be worked out and used in practice
- Providing support to front-line staff and managers in care homes to enable them to hold uncertainty and manage risk in people with severe memory problems to avoid unnecessary place of care transfers.
- Identifying, facilitating and supporting the training needs of care home staff in the care of those with severe memory problems.
- Recognising the needs of family carers, including being alert to possible anxiety and depression.
- Supporting the commissioning of effective and sustainable systems to deliver these objectives.

Overview of the intervention

The enhanced model of care delivered by the intervention will run for 6 months. For a detailed description of the intervention see Appendix 1. Facilitating effective clinical change in complex health and social care systems can be challenging. Compassion aims to set out a clear pathway of the actions that need to be taken, and by whom, for its effective implementation. This includes integrating change within existing systems to underpin current expertise and developing an understanding of what is needed for continued best practice. The key people involved in delivering Compassion for the pilot phase are listed below.

Interdisciplinary Care Leader (ICL)

The ICL will be a new post funded through the Compassion research project. The main responsibilities of the ICL will include:

- Developing an understanding of the health and social care professionals, pathways and services relevant to the care home residents with severe memory problems that are currently available.
- Working with the care home staff to identify and assess residents suitable for inclusion in the intervention.

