		
life
 
 • Quality of life • Resource Utilisation • Number of hospital admissions • Sentinel events • Use of parenteral feeding • Use of personalised care plans • Death in usual /preferred place of care 
If the resident dies:
 
 • Use of medication • Burdensome interventions • Adherence to individual care plan
--	--	---

*evaluation data which is already routinely collected within this setting and is required for national NHS and social care end of life care targets and key commissioning performance indicators

Enhanced care team process data

The ICL will record process data on a pro-forma to enable monitoring and evaluation of the enhanced service. These data will be collected on a monthly basis, it will be anonymised and not identifiable at the level of individual residents. These data give us information on the feasibility and acceptability of the intervention and will include:

- Number of residents reviewed by the enhanced care team
- Number of contacts with family carers (by phone and face to face)
- Attendance at team meetings
- Number of individual care plans made by the enhanced care team
- Referral to other specialists outside the care home, for example dietician, speech and language therapists, tissue viability nurses
- Education and training needs of care home staff and how these were addressed i.e., by individual training sessions, referral to online training resources

In addition the ICL will keep a reflective diary (carefully written to ensure anonymisation and confidentiality) recording their experiences of scoping for and implementing the intervention, including notes on care home dynamics, their interactions with the core and wider teams, the care being delivered by staff and any changes being observed that may not be captured by the outcome measures.

Care home level process data

This data will be collected on a monthly basis by the care home manager (to comply with the UK Data Protection Act 1998) in collaboration with the ICL. It will be anonymised and not identifiable at the level of individual residents. Much of this data should already be routinely

collected and is required by governance organisations and local health and social care commissioners in their assessment of whether services are meeting statutory key performance indicators. The ICL will document:

- Whether pain tools are being routinely used in the care home

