The Quality of Life in Late Stage Dementia Scale (QUALID): is a validated scale that assesses quality of life over the prior week (37). (See Appendix 9).

Resource Utilisation in Dementia (RUD)-lite: Resource Utilisation in Dementia (RUD)-lite: Is a short version of the RUD structured interview to assess costs of care including patient accommodation, informal care, community care and hospitalizations (38). (See Appendix 10).

Monthly follow up assessments

Participating residents will be reviewed every four weeks in the care home by the research team, for a maximum of six months, or until death. We will repeat measures: the generalist clinical assessment; Waterlow, Sterling, CMAI, NPI, BANS, PAINAD, SM-EOLD, QUALID, and the RUD-lite. We shall also record prospectively the number of acute hospital admissions, the reasons for these, “burdensome interventions” e.g. enteral feeding tubes (27) and “sentinel events”, defined as “new medical conditions that have the potential to lead to a significant change in health status and a shift in the goals of care” e.g. pneumonia, hip fracture (6). Prescription medications and use will also be collected.

Data collection post death

The Comfort Assessment in Dying with Dementia Scale (CAD-EOLD) (36) (See Appendix 11) will be completed with care home staff within 14 days of the resident’s death to assess their level of comfort and pain in the seven days prior to their death. Through a review of care home notes we shall record use of medication at the end of life (i.e. “just in case” prescribing, opiates, syringe drivers and artificial hydration or nutrition), sentinel events and burdensome interventions. We will examine adherence to any individual care plans which were made.

Outcomes for family carers

Data will be collected independently by the research team during face to face interviews at study entry within 14 days of the initial resident assessment and then every month, by post or over the telephone (family carers’ preference). If family carers are un-contactable for more than 2 months or withdraw from the study we will document the reason and aim to continue to include the person with severe memory problems in the study, unless the carer specifically withdraws their assent.

At project start

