Data will be collected at the start of the intervention, and at monthly time points until a resident dies or until the end of the intervention period (6 months). This will ensure a detailed understanding and, because of the mortality rates expected, minimize attrition. Data will be entered into a password protected anonymised database by the research team.

Quantitative analysis

We will use simple descriptive statistics to summarise process data and the outcomes collected by the ICL at the care home level (i.e. number of deaths in the last month etc.) We will describe the demographic and clinical characteristics of residents and family carers who participate in the data collection, as well as symptoms experienced, interventions received and any sentinel events. We will describe the symptom burden and quality of care received using SWEOLCD, QUALID. We will compare the scores to the results of our previous study in order to gain inferences on whether the enhanced care project makes a difference. The results will be summarised using mean and standard deviation or alternatives in case of non-normally distributed data. Appropriate plots will also be produced.

Qualitative analysis

The interviews will be audio-taped, transcribed verbatim and entered onto a qualitative software programme (Atlas-ti) for the coding, management and retrieval of data. Transcripts will be analysed and coded using Thematic Analysis. The data analysis process will follow the guidelines provided by Braun and Clarke (45) to develop meaningful themes and a rigorous approach to data analysis will be adopted by working to the quality framework recommended by Spencer (46). Throughout the analytic process, the researchers will engage in ongoing reflection with the use of memoing and reflective diaries to engage with the data further and refine emergent themes. Data triangulation will be achieved by interviewing both family carers and care home staff from a variety of work roles (i.e., care home manager, health care assistant, nurse) to explore the facilitators and barriers to the implementation of the enhanced model of care from different perspectives.

Final analyses

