After full data collection ends, we will undertake definitive analyses to detail the demographic features of the cohort and assess the symptom management and their health care needs (using Stirling, Waterlow, NPI and sentinel events), taking into account repeated measures on individual subjects. We shall describe the level and nature of unmet needs and examine descriptively (using mean and standard deviations or suitable alternatives in case of non-normally distributed data and graphs) how comfort and quality of life change over time (using PAINAD, SM-EOLD, SW-EOLD and QUALID). We will describe the trajectory of carer wellbeing (HADS and Zarit Buden Interview) during their friend/relative's final stages of life with severe memory problems and how this may change if the resident dies, using plots of the of wellbeing over time.

Sample size

This is a pilot study and as such a formal power calculation is not appropriate. Numbers are chosen on pragmatic grounds as sufficient to demonstrate feasibility in terms of recruitment and acceptance of the intervention. We will aim to recruit 30 residents with severe memory problems from two care homes from which to collect individual outcome data.

Health economics

Health economic evaluation will consider resource allocation in caring for patients with severe problems and, where relevant, in their last 6 months of life, as well as the quality of life of their family carers and associated economic impact on these family carers in this period.

Data on resource and service use for people with severe memory problems (RUD-Lite) and economic burden on family carers (Zarit Burden Interview) will be collected both at baseline and monthly after the enhanced care project has been implemented. These data will be collated with unit costs data from *Unit Costs of Health and Social Care (2012)* (47;48) to obtain costs per patient from NHS (such as averted hospital admission, costs for a typical episode), costs from personal social services (such as training and education for care home staff) and costs from societal perspectives (such as local commissioners' decisions on scarce resource allocation, additional costs to public purse where caring responsibilities had been met by the state instead of family carers).

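### The protocol does not secure a pre-intervention baseline: the order of baseline and service start is not fixed, and home-level event counts have one project-start reading

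*Protocol*

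**What the plan says.** **Timing of data.** Under Data analysis: "Data will be collected at the start of the intervention, and at monthly time points until a resident dies", or until the six-month intervention period ends. Table 4 has one project-start column followed by monthly points for six months, and no column for an earlier period.

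**Length of service and follow-up.** Overview of the intervention: "The enhanced model of care delivered by the intervention will run for 6 months". The section on monthly follow-up of residents says: "Participating residents will be reviewed every four weeks in the care home by the research team, for a maximum of six months, or until death".

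**Who starts the service.** The home's owner consents to the intervention for the whole home. Individual consent or assent is needed only for individual-level data and is a separate process. One of the ICL's own tasks is "Working with the care home staff to identify and assess residents suitable for inclusion in the intervention".

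**Order of baseline and service.** Health economics says that RUD-Lite and Zarit data "will be collected both at baseline and monthly after the enhanced care project has been implemented", which suggests a baseline before implementation. The section on recruiting family carers describes carers of residents to whom the service has already been given, which suggests the reverse.

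**Consent waits.** On the personal-consultee route (Consent Procedures, step 3) there is a 14-day wait for the reply slip, then one contact by the home, then: "If no assent form is returned within 14 days then the research team will telephone the personal consultee on the maximum of two occasions".

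**Home-level indicators.** Care home level process data: "This data will be collected on a monthly basis by the care home manager", working with the ICL. The list includes deaths in the last month, ambulance transfers and out-of-hours visits.

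**Use.** Objective 4: "Evaluate whether the enhanced model of care has an impact on a range of national key performance indicators and outcomes".

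**The concern.** The study has two homes and no concurrent control. For home-level indicators, any statement about impact must come from comparing the intervention months with what went before. The comparison with the previous study, under Quantitative analysis, is of scores; it does not extend to deaths, transfers or out-of-hours visits.

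Two things weaken the before side. First, the order of resident and carer baselines relative to ICL start is left open, and the text points both ways. If some baselines are taken after the service has begun to act, part of any early change is absorbed into the baseline, and those residents also have less than six months of service left to observe. Second, one month of a sparse count is dominated by chance and season. A project-start month that happens to be high or low would make six ordinary months look like an improvement or a deterioration.

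A missed baseline cannot be recovered for the individual scales. The home-level look-back depends on the records being requested.

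**Working it through.** **1. Consent lag.** The Protocol gives no figure for time from approach to baseline, so there is nothing to reproduce. The stated waits are:

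| Route | Stated wait | Source |
|---|---|---|
| Personal consultee, slip and form both late | 14 + 14 = 28 days before the final telephone reminders | Consent Procedures, step 3 |
| Personal consultee, prompt reply or signing in person | no fixed wait | step 3 |
| Professional consultee, next of kin documented but not reached | about 7 days of attempted contact, then the consultee's own procedure | step 5 |
| Resident with capacity | no fixed wait | step 1 |

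Six months is 365.25 / 2 = 182.6 days, so 28 / 182.6 = 15% of the intervention. This share is lost only on the slow route, and only if consent is not started before the ICL. The carer interview may follow the resident assessment by up to 14 days (Outcomes for family carers), giving 28 + 14 = 42 days, or 42 / 182.6 = 23%. That longer figure concerns the carer baseline only.

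**2. Pre-intervention data by outcome (Table 4).**

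| Outcome | Project start | Monthly |
|---|---|---|
| Care home level data | one entry | yes |
| RUD-Lite, which covers hospitalisations | one entry | yes |
| Burdensome interventions | none | yes |
| Sentinel events | none | yes |

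**3. Precision of a before/after rate ratio for home-level counts.** Inputs: 6 intervention months (Protocol); B baseline months, with B = 1 as planned and B = 6 or 12 as alternatives; event rate λ per month, which the Protocol does not give and which is *assumed* to be 2 or 3. For Poisson counts and a true ratio of 1, the 95% limits are the estimate multiplied and divided by

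exp(1.96 × √(1/(λB) + 1/(6λ))).

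- λ = 3, B = 1: √(1/3 + 1/18) = 0.624; factor 3.39
- λ = 3, B = 6: √(1/18 + 1/18) = 0.333; factor 1.92
- λ = 3, B = 12: √(1/36 + 1/18) = 0.289; factor 1.76
- λ = 2, B = 1: √(1/2 + 1/12) = 0.764; factor 4.47
- λ = 2, B = 6: √(1/12 + 1/12) = 0.408; factor 2.23
- λ = 2, B = 12: √(1/24 + 1/12) = 0.354; factor 2.00

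**4. Check with exact conditional (binomial) limits**, true ratio 1, rates again assumed and pooled over both homes:

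| Events per month | 1 baseline month | 3 months | 6 months |
|---|---|---|---|
| 2 | 0.22 to 9.20 | 0.35 to 3.25 | 0.41 to 2.43 |
| 4 | 0.34 to 3.97 | 0.48 to 2.19 | 0.54 to 1.84 |
| 8 | 0.47 to 2.45 | 0.60 to 1.71 | 0.66 to 1.52 |

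At 2 events a month the exact upper limit with one baseline month (9.20) is well above the approximate one (4.47), so the formula in step 3 is, if anything, kind to the single-month baseline. Most of the gain comes by six months; going from 6 to 12 adds little precision but covers a full year of season.

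**The case against.** The strongest reply is that the Protocol nowhere says baselines are late. It collects data at the start of the intervention, Table 4 separates project start from the period during the project, and the health economics text implies a baseline before implementation. This stands. A reader might infer that every resident is first measured after weeks of exposure, or that consent takes at least four weeks. The text supports neither: recruitment could precede the ICL, and the 14-day periods are reminder triggers, not minimum waits. What is left is an order that is not fixed and is described inconsistently.

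A reader might also infer that hospital admissions have no baseline. They have one, since RUD-Lite covers hospitalisations and is taken at project start. The gap is confined to sentinel events and burdensome interventions.

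It can also be said that the ICL begins with scoping local services and forming teams, so early exposure may be weak. That is plausible, and the size of any dilution cannot be shown from the document.

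Finally, this is a feasibility pilot with home-level data summarised descriptively. No before/after test is planned, the event rates above are assumed, and even twelve prior months leave a factor of 1.8 to 2.0 before allowing for overdispersion or for having only two homes. This limits the importance of the point. It does not remove it, because Objective 4 is still worded as impact on these indicators, and a descriptive display is also more informative with several prior months than with one.

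**Conclusion.** The point holds in a limited form. The Protocol does not secure a pre-intervention baseline: it sets no order between individual baselines and ICL start, its sections imply different orders, home-level counts have a single project-start month, and two event outcomes have no project-start entry.

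For individual measures, the possible lag is about 28 days (15% of six months) on the slow personal-consultee route and less elsewhere, and it matters only if consent is not started early. For home-level counts, at an assumed 2 to 3 events a month, the 95% factor falls from about 3.4 to 4.5 with one baseline month to 1.9 to 2.2 with six. These figures assume Poisson counts with a constant rate; overdispersion and having two homes would widen all of them.

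This is a minor-to-moderate improvement to a descriptive pilot. A reader might infer that a better baseline would make Objective 4 answerable. With two homes and no control it would not; it would make the description less dependent on one month's chance.

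**What to change.** 1. **Home-level look-back (the main gain).** From the starred items in Table 3, which the Protocol describes as already routinely collected, extract the 6 to 12 months before ICL start in each home, with monthly resident numbers as denominator. Show them beside the six intervention months, descriptively. Confirm first which items each home actually holds, since the Protocol says elsewhere only that much of this information should be available.
2. **Sequence.** State that resident and carer baselines are completed before the ICL starts in each home where possible, with consent begun once the owner agrees. For later entrants, record days from ICL start to baseline and show them separately. Reconcile the wording in the carer recruitment section, the opening of Data analysis, and Health economics.
3. **Optional.** Record sentinel events and burdensome interventions over a stated look-back period from the GP notes already read at entry. Treat this as description only: residents are selected as alive at entry, so the look-back and follow-up periods are not comparable.

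Cost: one retrospective extraction per home, one extra date variable, and possibly a slightly later ICL start.

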 - a. Enhanced care team
 - b. Care home environment and management
 - c. Care home staff
 - d. Family carers
 - e. Residents with severe memory problems

5. Attempt to describe in detail the costs of delivering the intervention at our pilot sites and the costs of each of its sub-components to inform the commissioning process. These costs can be set against potential benefits and recommendations made

RECRUITMENT AND CONSENT PROCEDURES

Location

Through our previous cohort study we have worked with care homes in the Camden and Barnet Commissioning Group areas. We have chosen these as sites for our pilot intervention because we have previous experience of working with local clinicians including GPs and palliative care teams and they represent different location in terms of the socioeconomic and demographic composition of the area.

Recruitment of care homes

After gaining ethical consent for the study we will approach each care home manager by sending them a letter with brief study details. If the manager is interested, senior study staff will then visit the care home and provide further information regarding the project. We will, at the same time, also approach the proprietor or owner of the care home with similar information and seek their written consent for the home to participate in the enhanced care service and the collection of data from the home for the project outcomes.

Consent for implementing the enhanced model of care within the care home

We will be implementing our intervention of the enhanced care model at the level of the care home; our study can therefore be defined as a cluster pilot evaluation. The model of individual informed consent (or nominee assent) to receive the intervention may not be appropriate for a number of reasons. Firstly we are working with existing clinical services to offer an enhancement of usual care which is in line with the recent English Government Dementia and End of life care strategies. Secondly, we will be training and supporting the existing team to enhance and optimise practice, and thus may influence the care of all residents of the home.

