The research staff collecting data will be given training and supervision on all of the study assessment tools and family carer interview schedule. The research team will review their recruitment procedures after one month. Any problems will be documented. If substantial

changes to the protocol are needed we will seek approval of proposed changes from the Research Ethics Committee.

If we discover issues of malpractice, maltreatment or serious neglect, to the degree that the relevant local authority's safeguarding procedures are triggered, we will in this circumstance be required to break patient confidentiality and inform the relevant authorities, following whichever standard local authority safeguarding procedures are in operation.

It is important that issues of sustainability are considered so that we do not leave the care home unsupported after the enhanced care pilot has finished. Evidence suggests that even after the research team have finished the pilot, benefits may persist and that local services maintain and further develop new interventions, so maintaining on going improvements in care; "dynamic sustainability" (28). One aspect to sustain any benefits is that participating nursing homes will be provided with a structured training programme designed to meet any training/care needs identified during the cohort study.

PROJECT INTERVENTION

Preparing the Compassion Intervention manual for the enhanced model of care

We have produced a written document to describe Compassion in manual form as recommended by the Medical Research Council (MRC) guidance on the development of complex healthcare interventions 2008. This provides a framework by which the intervention can be sustained and becomes replicable at a number of sites. It describes for participating partners the core intervention components and the steps required to implement components. There are two core components:

1. Facilitation of integrated care for people with severe memory problems and their family carers.
2. Education, training and support for health and social care professionals at all levels and for family carers.

The manual in its development was reviewed by key stakeholders during a focus group (care home managers, representatives from palliative care, GPs and care of the elderly physicians). Necessary changes were made, and further amendments were made by the programme grant expert steering group.

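### The protocol plans to infer from a comparison with an earlier study whether the intervention makes a difference, but two treated homes without a control cannot separate an effect from home or period

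*Protocol*

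**What the plan says.** The section on consent for implementing the model explains that the intervention is applied at the level of the home, and concludes that "our study can therefore be defined as a cluster pilot evaluation". The aims section places it "in two care homes in two different health and social care economies; one in the Camden Commissioning Group and one in the Barnet Commissioning Group". Both homes receive the intervention and no control home is described.

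The target is pragmatic: "We will aim to recruit 30 residents with severe memory problems from two care homes". The Sample size section gives no power calculation, effect size, SD or ICC.

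Under Quantitative analysis, symptom burden and quality of care are described with a satisfaction-with-care score and QUALID. The next sentence is: "We will compare the scores to the results of our previous study in order to gain inferences on whether the enhanced care project makes a" (final word, difference, omitted). Results are summarised by mean and SD or alternatives, with plots.

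Under Final analyses, symptom management and needs (Stirling, Waterlow, NPI, sentinel events) are analysed "taking into account repeated measures on individual subjects". Comfort and quality of life over time are examined descriptively. The care-home level is mentioned only for process data and outcomes collected by the care leader, and home appears in no resident or carer analysis.

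**The concern.** The stated purpose of the historical comparison is a conclusion about effect. Residents of one home share staff, GP cover and management, and the whole home receives the service at once. Every pilot score is therefore tied to one of two homes and to one calendar period. A difference from the earlier study can arise from the homes or from the period with no contribution from the intervention.

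The protocol itself gives reason to expect homes to differ. Among the reasons for choosing the two areas is that "they represent different location in terms of the socioeconomic and demographic composition of the area".

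The synopsis says the pilot is to inform a definitive trial. Objective 4 asks whether the model has an impact on outcomes, and objective 5 would set costs against potential benefits for commissioners. A home or period difference read as benefit would carry into both.

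**Working it through.** There is no stated calculation to reproduce, because 30 is a pragmatic number. The checks below show what two homes can support.

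**Inputs from the protocol.** 30 pilot residents; 2 homes; an earlier cohort with 57 residents in care homes (work stream 1).

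**Assumptions not in the protocol.** The previous study is that cohort; 15 residents per home; ICC 0.01 to 0.10; 2 to 14 cohort homes of equal size, none of them a pilot home; a two-sided 5% t-test.

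**1. Information in 30 residents.** Design effect = 1 + (15 - 1) × ICC. At ICC 0.05 this is 1 + 14 × 0.05 = 1.70, and the effective sample is 30/1.70 = 17.6.

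**2. Chance shift of a two-home mean.** SD of the shift = √(ICC/2). At ICC 0.05 it is √0.025 = 0.16 outcome SDs. This needs no test and would affect anyone comparing two means.

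**3. Error rate if residents were tested as independent.** Example with ICC 0.05 and four cohort homes of 57/4 = 14.25 residents:
- Cohort design effect = 1 + 13.25 × 0.05 = 1.66.
- Variance assumed: 1/30 + 1/57 = 0.0509.
- Actual variance: 1.70/30 + 1.66/57 = 0.0858.
- SE ratio = √(0.0858/0.0509) = 1.30.
- Rejection rate = 2 × [1 - Φ(1.96/1.30)] = about 13%.

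Simulated t-tests (6,000 per setting) give 14% for the same case. The ranges in the table cover formula and simulation.

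**4. Whether allowing for clustering rescues the inference.** A home-level analysis of the pilot mean has 2 - 1 = 1 degree of freedom, so t = 12.7. Expected 95% half-width = 12.7 × √(design effect/30) × √(2/π). Treating residents as independent gives 2.05/√30 = 0.37 SD.

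| ICC | Design effect | Effective n | SD of shift | Rejection rate as if independent | Home-level half-width (SD) |
|---|---|---|---|---|---|
| 0.01 | 1.14 | 26.3 | 0.07 | 6-7% | 1.98 |
| 0.05 | 1.70 | 17.6 | 0.16 | 11-17% | 2.41 |
| 0.10 | 2.40 | 12.5 | 0.22 | 17-25% | 2.87 |

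A half-width of 2 SD or more is uninformative. These figures cover chance differences between homes only. They contain nothing for calendar period, nor for the different entry criteria (FAST 7a and above in the cohort, 6a and above plus a clinical criterion in the pilot), which are a separate matter.

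**The case against.** The best defence is that the plan is descriptive: means, SDs and plots, with no p-value, interval or significance level. The sample size was chosen for feasibility, and display by home may be left to an SAP. This stands as far as the numbers go. No standard error is planned, and clustering barely changes an SD: at ICC 0.05 the expected pooled variance is (30 - 1.70)/29 = 0.976 of the true one, so the SD is about 1% low. It does not answer the sentence that sets the purpose of the comparison as inference about effect. That sentence is in the protocol, and no SAP method can make two treated homes support it.

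Several stronger readings are tempting but not supported:
- *The plan pools residents and will show nothing by home.* It is silent on home; pooling is an inference from that silence.
- *The historical comparison allows only for repeated measures.* That clause belongs to the Final analyses of other outcomes. The historical comparison names no method.
- *The study has a false-positive rate of some 12%.* No test is planned. Moreover, satisfaction with care is a carer score and the cohort had 26 carers, so 30 against 57 does not describe it.
- *Comparing the two care economies is the aim.* The aim is to understand how the model "operates in practice in two care homes in two different health and social care economies"; none of the five objectives compares the homes.
- *The pilot homes were in the cohort.* The team had worked with homes in both areas, and "participating nursing homes will be provided with a structured training programme designed to meet any training/care needs identified during the cohort study". That suggests overlap without establishing it. Overlap would reduce the home component but not the period component.

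The plan also contains a useful within-home contrast. QUALID and satisfaction with care are taken at project start and monthly (Table 4), and change over time is to be examined. Stable home differences largely cancel in that change. Decline, deaths and other changes over six months do not, so it too remains descriptive.

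**Conclusion.** The concern holds in a limited form. The protocol fixes an inference about effect from a comparison in which intervention, home and period cannot be separated. This follows from the design alone (two treated homes, no concurrent control, an earlier study as comparator) and needs no assumed ICC. Adjustment for clustering is not the remedy, because one degree of freedom leaves nothing usable.

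The size can only be illustrated: a chance shift of 0.07 to 0.22 SD in the two-home mean, and rejection rates of about 6-7%, 11-17% and 17-25% at ICC 0.01, 0.05 and 0.10 if someone applied a t-test to residents as independent. These rest on the assumed ICC, number of cohort homes, equal split and test. The point matters for what the pilot may conclude; its feasibility and acceptability objectives are unaffected.

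**What to change.** In the Quantitative analysis section, replace the clause that states the purpose of the comparison with wording such as:

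> Scores will be set beside those of the earlier study as descriptive context. Two homes without a concurrent control do not allow an inference about the effect of the intervention.

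Then:
- Present resident and carer scores by home as well as overall, and as change from project start. The baseline is already collected (Table 4).
- If a pilot home also took part in the earlier cohort, and the earlier data can be identified by home, show that home's earlier scores beside its pilot scores.
- Give no p-value or interval that treats residents as independent.

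The cost is a few sentences, a home identifier in the pilot dataset and a more modest conclusion. By-home figures will be imprecise, at about 30/2 = 15 residents each if recruitment splits equally. The same-home display depends on records that the protocol does not show to be available, so it should stay conditional.
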